9.7.1.8.3 LABORATORY VALUES

Laboratory results will be summarized using International System of Units, as appropriate. For all quantitative parameters listed in [Section 9.5.1.5.3](#), the actual value and the change from baseline to each postbaseline visit and to the end of treatment (defined as the last on-treatment value) will be summarized by visit and treatment group using descriptive statistics. Qualitative parameters listed in [Section 9.5.1.5.3](#) will be summarized using frequencies (number and percentage of subjects), and changes from baseline to each postbaseline visit and to end of treatment will be reported using shift tables. Percentages will be based on the number of subjects with both nonmissing baseline and relevant postbaseline results.

Laboratory test results will be assigned a low/normal/high (LNH) classification according to whether the value was below (L), within (N), or above (H) the laboratory parameter's reference range. Within-treatment comparisons for each laboratory parameter will be based on 3-by-3 tables (shift tables) that compare the baseline LNH classification to the LNH classification at each postbaseline visit and at the end of treatment. Similar shift tables will also compare the baseline LNH classification to the LNH classification for the highest and lowest value during the treatment period.

Appendix 1 (Sponsor's Grading for Laboratory Values) presents the criteria that will be used to identify subjects with treatment-emergent markedly abnormal laboratory values (TEMAVs). Except for phosphate, a TEMAV is defined as a postbaseline value with an increase from baseline to a Grade of 2 or higher. For phosphate, a TEMAV was defined as a postbaseline value with an increase from baseline to a Grade of 3 or higher. When displaying the incidence of TEMAVs, each subject may be counted once in the laboratory parameter high and in the laboratory parameter low categories, as applicable.

Lymphocyte subsets (ie, CD4 [T helper cells], CD8 [cytotoxic T cells], CD19 [B cells], CD16/CD56 [natural killer cells] and CD14 [macrophages]) and regulatory T cells will be summarized in the same manner as other laboratory parameters. Mean lymphocyte subsets and the mean change from baseline in lymphocyte subsets will also be displayed graphically over time by dose.

Serum IgG, IgM, and IgA will be measured and summarized in the same manner as other laboratory parameters.

9.7.1.8.4 VITAL SIGNS

Descriptive statistics for vital signs parameters (ie, systolic and diastolic BP, pulse, respiratory rate, temperature, weight), and changes from baseline will be presented by visit and treatment group.

9.7.1.8.5 ELECTROCARDIOGRAMS

Descriptive statistics for ECG parameters and changes from baseline will be presented by visit and treatment group. Shift tables will present changes from baseline in ECG interpretation (categorized as normal; abnormal, not clinically significant; and abnormal, clinically significant) to the end of treatment.

In addition, the number (percentage) of subjects with at least 1 postbaseline abnormal ECG result in QTcF during the treatment period will be summarized. Clinically abnormal ECG results in QTcF will be categorized as follows:

Absolute QTc interval prolongation:

- QTc interval >450 msec
- QTc interval >480 msec
- QTc interval >500 msec

Change from baseline in QTc interval:

- QTc interval increases from baseline >30 msec
- QTc interval increases from baseline >60 msec

9.7.1.8.6 OTHER SAFETY ANALYSES

Cognitive decline will be assessed as a safety assessment, in addition to efficacy assessments. Cognitive assessments will include the ADAS-cog₁₄, MMSE, CDR, and CBB (see [Section 9.7.1.6](#)).

9.7.2 Determination of Sample Size

9.7.2.1 Sample Size Rationale in the MCI/Prodromal Cohort

Primary endpoint – derived ADCOMS

The sample size and design characteristics to test the hypothesis for the primary objective based on the primary endpoint, change from baseline of the derived ADCOMS at 18 months, were determined by means of simulations. Extensive study simulations have shown that a total of 500 subjects will be sufficient to demonstrate that the most likely ED₉₀ dose achieves a 25% improvement over placebo with a probability of at least 80% in the interim and final analyses. There is at least a 90% probability of study success for the dose response scenarios where treatment was considered to have a clinically meaningful treatment effect. Simulations have also shown that if there is no obvious dose effect, the probability of falsely claiming superiority to placebo is at most 5%.

For each of the 4 treatment groups (3 active doses and placebo) the final number of subjects per group will differ depending on the observed interim treatment responses. The simulation plan will be an appendix to the statistical analysis plan and will present further details.

vMRI

The null hypothesis is that there is no difference between active dose and placebo. There are 3 null hypotheses corresponding to 3 active doses. The alternative hypothesis is that at least 1 null hypothesis is false (1-sided). The null hypotheses will be tested using Dunnett's method with 1-sided alpha of 0.05. The statistical power was estimated through simulation for a moderate dose-response assumption that the percent reduction in change from baseline of total hippocampal volume compared with placebo would be 15%, 20%, and 25% corresponding to the 3 doses, respectively. The estimated power for the actual planned study sample size is 78% at 18 months assuming an attrition rate of 20% at 18 months. Under a stronger dose-response assumption (ie, the percent reduction in change from baseline of total hippocampal volume compared with placebo is twice as much as that in the moderate dose-response assumption), the estimated power is at least 99% at 18 months.

Amyloid PET

The null and alternative hypotheses and the statistical test are the same as those for vMRI. To estimate the sample size for the amyloid PET imaging subgroup at 18 months, a common SD of the change from baseline was estimated at 0.33 and a reasonable mean difference between treatment and placebo was estimated as 0.25 (standardized uptake value ratio [SUVR]). Assuming a moderate dose-response, the best dose would achieve a difference of 0.25 (SUVR) and the middle and low doses would achieve a difference of 0.2 and 0.15 (SUVR), respectively; this would require a total of 100 subjects from all 4 arms at 18 months to achieve 80% power.

9.7.2.2 Sample Size Rationale for the Mild to Moderate AD Cohort (revised per Amendment 01)

ADCOMS at Month 18

The null hypothesis is that there is no difference between active dose and placebo. There are 2 null hypotheses corresponding to 2 active doses. The alternative hypothesis is that at least 1 null hypothesis is false. The null hypotheses will be tested using Dunnett's test with 2-sided alpha of 0.05 as described for the Mild to Moderate AD cohort in [Section 9.7.1.6.2](#). The statistical power was estimated through simulation for the dose-response assumption that the percent reduction in change from baseline of ADCOMS at 18 months compared with placebo would be 33% and 50% corresponding to the 2 doses, respectively. The estimated power for the actual planned 200 mild to moderate AD subjects is approximately 80% assuming a 2-sided alpha of 0.05. (revised per Amendment 01)

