9.7 Statistical Methods

All statistical analyses will be performed by the sponsor or designee. Statistical analyses will be performed using SAS software or other validated statistical software as required.

All statistical tests will be based on the 5% (2-sided) level of significance, except for the Bayesian methods on the primary endpoint.

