9.7.1.6.2 SECONDARY EFFICACY ANALYSES

The MCI/Prodromal Cohort

An MMRM will be used to analyze the following secondary endpoint: (revised per Amendment 02)

- Change from baseline in total hippocampal atrophy at 12 and 18 months of treatment in MCI/Prodromal subjects as measured by vMRI

Comparisons between each treatment group and placebo will be performed.

The Mild to Moderate AD Cohort (revised per Amendment 01)

The MMRM will be used to analyze the change from baseline of derived ADCOMS at 18 months in mild to moderate AD. If there is no treatment group-by-population interaction in the overall study, the MMRM analysis will include all subjects (MCI/Prodromal or mild to moderate AD) in the overall study. Otherwise, the MMRM analysis will only include subjects in the Mild to Moderate AD cohort. The comparison between placebo and active doses will be performed within mild to moderate AD subjects regardless of subjects included in the MMRM analysis. Dunnett's method will be used to control for multiplicity due to multiple comparisons.

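### Hippocampal vMRI and amyloid PET are tested and powered at one-sided 5%, although section 9.7 sets every test outside the Bayesian primary at two-sided 5%; under that rule the PET power is about 71%, not 80%

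*Protocol*

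**What the plan says.** The general rule is in Protocol section 9.7 and is repeated in the synopsis under Statistical Methods: "All statistical tests will be based on the 5% (2-sided) level of significance, except for the Bayesian methods on the primary endpoint".

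Section 9.7.2.1 (vMRI), repeated in the synopsis, sets a different rule for total hippocampal volume in the MCI/Prodromal cohort. "There are 3 null hypotheses corresponding to 3 active doses", the alternative is expressly one-sided, and "The null hypotheses will be tested using Dunnett's method with 1-sided alpha of 0.05". The assumed percent reductions "compared with placebo would be 15%, 20%, and 25% corresponding to the 3 doses, respectively", and the estimated "power for the actual planned study sample size is 78% at 18 months assuming an attrition rate of 20% at 18 months".

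For amyloid PET, the same section says "The null and alternative hypotheses and the statistical test are the same as those for vMRI". It assumes an SD of 0.33 SUVR and differences of 0.15, 0.20 and 0.25 SUVR, and concludes that 100 subjects over four arms give 80% power.

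The analysis section for vMRI, 9.7.1.6.2, names the MMRM and adds "Comparisons between each treatment group and placebo will be performed". It gives no alpha, side or adjustment for this endpoint. For the mild to moderate AD cohort, 9.7.1.6.2 names Dunnett and section 9.7.2.2 sets it at two-sided 0.05.

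**The concern.** vMRI and PET are frequentist analyses of non-primary endpoints, so the single exception in section 9.7 does not reach them. Section 9.7.2.1 is also more than a sizing assumption, since it says how the hypotheses will be tested. The protocol therefore gives two answers to whether a given result is significant. With three doses against placebo, a Dunnett statistic between about 2.09 and 2.39 (96 degrees of freedom, PET) or about 2.07 and 2.36 (396 degrees of freedom, vMRI) passes one rule and fails the other.

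Hippocampal atrophy is the only secondary endpoint in the primary population. Section 9.2.5.4 looks to it for support that effective treatment modifies the disease course, and section 7 intends the study to be supportive for registration. If the side is left open until the data are unblinded, the choice can decide whether that support is claimed. The quoted powers belong to the easier of the two tests.

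**Working it through.** **Method.** For dose j against placebo (0):

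t_j = (mean_j − mean_0) / [s × √(1/n_j + 1/n_0)], with pooled s and N − 4 degrees of freedom, signed so that benefit is positive.

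One-sided Dunnett rejects when the largest t_j exceeds c1. Two-sided Dunnett rejects when the largest |t_j| exceeds c2. Power is the probability of rejecting at least one of the three nulls, which matches the protocol's alternative hypothesis. Critical values and powers were simulated.

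**PET: reproducing the plan's figure.** Inputs from section 9.7.2.1 are SD 0.33, differences 0.15, 0.20 and 0.25, and N = 100. The 25 per arm agrees with the scanning target in section 9.5.1.4.2.

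- Standard error of a difference: 0.33 × √(2/25) = 0.0933.
- Expected t for the three doses: 0.15/0.0933 = 1.61; 0.20/0.0933 = 2.14; 0.25/0.0933 = 2.68.
- One-sided 5%: c1 = 2.087, power 81.2%. At 24 per arm it is 79.6%, so 25 per arm is the smallest balanced design that reaches 80%. The plan's figure is reproduced.

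**PET: the section 9.7 rule.**

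- Two-sided 5%: c2 = 2.386, power 71.1%.
- Loss: 81.2 − 71.1 = 10.1 points, or about 9 below the stated 80%.
- The observed difference needed rises from 2.087 × 0.0933 = 0.195 to 2.386 × 0.0933 = 0.223 SUVR.
- Reaching 80% two-sided takes about 31 per arm (80.9%; 30 per arm gives 79.3%), or 4 × 31 = 124 in total.

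**vMRI: only the size of the loss can be checked.** The protocol gives neither the SD nor the placebo change. As an assumption, 500 × 0.80 = 400 completers, 100 per arm, with effects in the ratio 15:20:25 scaled so that one-sided power equals the stated 78%. This corresponds to an SD of about 0.70 of the placebo change. As a check on the scaling, doubling the effects gives more than 99.9% one-sided, which agrees with the plan's claim of at least 99%.

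| Assumption | One-sided 5% | Two-sided 5% | Loss (points) |
|---|---|---|---|
| 100 per arm, scaled to 78% | 78.0% | 67.5% | 10.5 |
| 130/50/90/130, rescaled to 78% | 78.0% | 67.6% | 10.4 |
| 150/50/50/150, rescaled to 78% | 78.0% | 67.6% | 10.4 |
| 100 per arm, scaled to 78% for the best dose only | 78.0% | 68.6% | 9.4 |
| 140/60/60/140, SD held at 0.70 of placebo change | 86.1% | 78.0% | 8.1 |

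Arms are listed from placebo upward. The loss stays between about 8 and 11 points. The level does not: two-sided power is 67% to 69% when the variance is re-solved to match 78% for each split, but 78% at 140/60/60/140 with the SD held fixed. Under the doubled effect at 100 per arm, two-sided power is still 99.9%.

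**The case against.** The best defence is that nothing is miscalculated: 78% and 80% are correct for the test stated beside them. The specific rule may be meant to override the general one. A directional alternative is stated, section 9.2.5.4 predicts slower atrophy, and adding vMRI and PET to the exceptions in section 9.7 would also remove the conflict. All of this stands, except that the protocol does not say which rule governs, and section 9.7 words its exception so that only the Bayesian primary methods qualify.

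It also stands that the consequences are limited. The 500-subject size, early success, futility and adaptive randomization all rest on ADCOMS. PET is exploratory, and 100 is a minimum for one ligand. If two ligands each gave 25 per arm and were pooled, which the protocol does not say, two-sided power would be about 95%.

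Four stronger readings are tempting and are not supported:

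- A reader might infer three competing tests for vMRI. Section 9.7.1.6.2 states no alpha, side or adjustment, so it contradicts neither rule. Two statements conflict.
- A reader might infer three unadjusted two-sided tests, with a familywise error near 12.5%. That requires ignoring section 9.7.2.1, which prescribes Dunnett. Only the side is in dispute.
- A reader might infer that faster atrophy on drug would go unseen. A one-sided test cannot declare it significant, but the MMRM comparisons with placebo still estimate it.
- A reader might take 67% as the true vMRI power. It is back-solved from the sponsor's own 78% and moves with the allocation.

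**Conclusion.** The contradiction holds and should be fixed, though it is not critical to the trial. Sections 9.7 and 9.7.2.1 give incompatible significance rules for one secondary and one exploratory endpoint, and the synopsis repeats both. Judged by section 9.7, PET power at 100 subjects is about 71% instead of 80%. This rests only on the protocol's inputs, equal arms and power defined as detecting any dose. The vMRI power falls by roughly 8 to 11 points from its one-sided value. That size rests on assumed completer numbers and an assumed variance, and the absolute figure cannot be recovered from the protocol. The Bayesian primary analysis is untouched.

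**What to change.** In section 9.7.2.1 and the matching synopsis text, replace the one-sided 0.05 Dunnett test by two-sided 5% Dunnett and make the alternative hypothesis two-sided. This follows section 9.7 and the test already set for the mild to moderate AD cohort. Name the same test for vMRI in 9.7.1.6.2 and for PET in 9.7.1.6.3.

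Restate PET power as about 71% at 100 subjects. For vMRI, have the sponsor rerun its own simulation two-sided, with its hippocampal SD and expected adaptive allocation. About 67% is a guide only, under 100 completers per arm with variance calibrated to the stated 78%.

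If the sponsor prefers a one-sided test, section 9.7 must list it as an exception and justify it. Both rules cannot remain.

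The cost is wording, one simulation rerun and a less favourable stated power. No subjects are added. Keeping 80% for PET would be a separate choice, at about 124 − 100 = 24 more 18-month scans.

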9.7.3 Interim Analysis

In order to make decisions about the remainder of the study as well as the full E2609 clinical development program, the sponsor will unblind safety, PK, and PD data on an ongoing basis and perform interim analyses of these data. Investigators, other clinical site staff, subjects and caregivers/informants will remain blinded to study treatment. (revised per Amendment 03)

An interim safety analysis will also be conducted when the first 60 subjects have completed 12 weeks of treatment (or discontinue study drug early) in Stage A. (revised per Amendments 01 and 03)

The MCI/Prodromal Cohort

The Bayesian interim analyses and response adaptive randomization will be conducted by an unblinded external independent analysis group in accordance with the protocol. Oversight of the Bayesian interim analyses and response adaptive randomization will be conducted by an independent unblinded committee that has expertise with Bayesian adaptive design in clinical studies to ensure that the response adaptive randomization process and interim analyses perform as expected. The analysis group will provide the interim analysis outcomes to the

committee at each interim analysis. The committee will ensure the integrity of the interim analysis and response adaptive randomization process through review of efficacy data. In addition, the committee will act in an independent advisory capacity to monitor the Bayesian interim analysis outcomes according to the early success and futility boundaries prespecified in the protocol. The committee will not be charged with any subject safety issues; this will remain the responsibility of the DSMB.

If the predefined early success criteria are met during the recruitment period, further recruitment and enrollment of MCI/Prodromal subjects into the study will stop (following confirmation from the Sponsor's Senior Management) and all currently randomized subjects will complete the full 18 months of treatment. No further interim analyses will be conducted after achieving early success.

If the predefined threshold for futility is reached, no additional subjects will be randomized into the study and the treatment of subjects already randomized into the study will stop and the study will be declared as "failed". All subjects will be monitored for safety for 3 months following their last dose.

If neither early success nor futility is reached and the study reaches full randomization, all subjects will complete 18 months of treatment. Interim efficacy analyses will be conducted every 3 months after full randomization is reached to assess futility and early success until all subjects complete 18 months of treatment. After full randomization, all study subjects will stop treatment only in the event of futility.

The DSMB will continue to monitor the safety aspects of the study throughout Stage A and Stage B. Details will be provided in the DSMB Charter. The study may be stopped for safety at any time.

The first Bayesian adaptive interim analysis will be conducted when 100 MCI/Prodromal subjects have been randomized into the study (ie, including MCI/Prodromal subjects from Stage A and Stage B). (revised per Amendment 01) Further interim efficacy analyses will be conducted after each additional 50 MCI/Prodromal subjects have been randomized, to a maximum of 500 MCI/Prodromal subjects (ie, at 100, 150, 200, 250, 300, 350, 400, 450, 500 subjects randomized). If the study reaches full randomization, additional interim analyses will be conducted every 3 months until all subjects complete 18 months of treatment. The study will be monitored for futility at each interim analysis. Starting at the interim analysis for 200 subjects, the study will be monitored for success at each interim analysis. Each interim analysis will be conducted on data for the derived ADCOMS.

In addition, at each interim efficacy analysis, response adaptive randomization will be used to update the allocation of new subjects between placebo and active doses according to a predefined automated algorithm.

The Mild to Moderate AD Cohort (revised per Amendment 01)

A group sequential design will be used for the Mild to Moderate AD cohort. (revised per Amendment 01) This design includes 3 looks, 2 interim looks (when 60% and 80% information fractions are achieved) and 1 final look. The information fraction is the number of assessments in all treatment arms divided by the total number of expected assessments. Interim analyses will be performed after the MCI/Prodromal cohort crosses the early success boundary. The corresponding efficacy boundaries will be 0.076, 0.022, and 0.0423 for the first, second, and final analyses, respectively. If the actual information fraction during the interim analyses is different from 60% or 80% at the interim, the efficacy boundaries will be adjusted based on the actual information fraction.

If early success in the MCI/Prodromal cohort is not achieved before the final analysis that is performed when all subjects have completed 18 months treatment, then only a final analysis will be performed in mild to moderate AD subjects. In the event of futility in the MCI/Prodromal cohort, an analysis will be performed for the Mild to Moderate AD cohort based on the data for mild to moderate AD subjects available at that time. (revised per Amendment 01)

Randomization into the Mild to Moderate AD cohort will remain at a fixed schedule throughout Stage B. (revised per Amendment 01)

The interim analyses in the Mild to Moderate AD cohort will be conducted by an independent analysis group. (revised per Amendment 01)

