All mild to moderate AD subjects will be included in the efficacy evaluations of the Mild to Moderate AD cohort. The analysis of the Mild to Moderate AD cohort is based on the group sequential design. Interim analyses in the Mild to Moderate AD cohort will only be performed after the MCI/Prodromal cohort crosses the early success boundary. The early efficacy signal based on the change from baseline of ADCOMS at 18 months is defined as crossing the interim-analysis boundaries for overwhelming efficacy in the mild to moderate AD population. The O'Brien-Fleming (OF) boundaries based on Lan-DeMets alpha spending function will be used to assess overwhelming efficacy. The corresponding OF boundaries based on P values will be 0.076, 0.0221, and 0.0423 for the first, second, and final analyses, respectively, according to 2 planned interim analyses at the 60% and 80% information fraction. (revised per Amendment 01)

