9.7.4 Other Statistical/Analytical Issues

Adaptive Randomization in the MCI/Prodromal Cohort

Randomization to placebo or 1 of 3 dose groups of E2609 will be fixed for the first 100 MCI/Prodromal subjects randomized in the study (1:1:1:1; placebo to each of the 3 active doses for the first 100 MCI/Prodromal subjects randomized, including those randomized from both Stage A and Stage B). Thereafter, randomization probabilities to each treatment group will be updated at each interim analysis, such that the randomization probability will be increased for the placebo group and dosage groups that represent the potential target dose (ED₉₀), and simultaneously decreased for other active arms. (revised per Amendment 01)

Randomization in the Mild to Moderate AD Cohort (revised per Amendment 01)

In Stage A, the mild to moderate AD subjects will be randomized to placebo or 1 of 3 E2609 dose groups (5, 15, and 50 mg of E2609) at a 1:1:1:1 ratio, while in Stage B, the mild to moderate AD subjects will be randomized to placebo or 1 of 2 E2609 dose groups (15 and 50 mg E2609) at a 1:1:1 ratio. (revised per Amendment 01)

Stratification (revised per Amendment 01)

Within the 2 clinical cohorts (MCI/Prodromal and mild to moderate AD), subjects will be stratified at randomization by *ApoE4* status (positive or negative) and prior treatment with AChEIs or memantine or both (yes or no). (revised per Amendment 01)

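### The mild to moderate AD information fraction is not tied to the 18-month outcome or the compared arms, so the interim boundaries can be looser than the data support

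*Protocol*

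**What the plan says.** For the mild to moderate AD cohort, Protocol section 9.7.3 sets a group sequential design: "This design includes 3 looks, 2 interim looks (when 60% and 80% information fractions are achieved) and 1 final look". It then fixes how information is measured: "The information fraction is the number of assessments in all treatment arms divided by the total number of expected assessments". If the actual fraction differs from 60% or 80%, the boundaries are to be recomputed from the actual fraction, which means this same quantity.

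The test itself is narrower:

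- Section 9.7.1.6: "The early efficacy signal based on the change from baseline of ADCOMS at 18 months is defined as crossing the interim-analysis boundaries", and the O'Brien-Fleming "boundaries based on Lan-DeMets alpha spending function will be used to assess overwhelming efficacy".
- Section 9.7.1.6.2: "The MMRM will be used to analyze the change from baseline of derived ADCOMS at 18 months in mild to moderate AD", with Dunnett's method for the comparisons with placebo.
- Section 9.7.2.2: two null hypotheses, one per active dose. "The estimated power for the actual planned 200 mild to moderate AD subjects is approximately 80% assuming a 2-sided alpha of 0.05".
- Section 9.7.4: "In Stage A, the mild to moderate AD subjects will be randomized to placebo or 1 of 3 E2609 dose groups". Stage A therefore adds some 5 mg subjects who are in neither powered comparison.

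The boundaries are printed as: "The corresponding efficacy boundaries will be 0.076, 0.022, and 0.0423 for the first, second, and final analyses, respectively". Section 9.7.1.6 gives the same figures, with 0.0221 for the second look. AD-cohort looks take place only after the MCI/Prodromal cohort has crossed its early success boundary.

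**The concern.** Alpha spending holds the error rate only if the fraction fed into the spending function tracks the information in the contrast being tested. Here a week-12 assessment counts as much as a week-78 assessment, and nothing limits the count to ADCOMS at 18 months or to placebo, 15 mg and 50 mg. Because early visits accumulate first, the fraction runs ahead of the 18-month data. Recomputing the boundaries does not help, since it uses the same fraction.

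Two things are at stake. Alpha may be spent too early. And a claim of overwhelming efficacy at 18 months could rest on few 18-month outcomes.

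**Working it through.** **Inputs.** Looks, boundaries and spending function: sections 9.7.1.6 and 9.7.3. Alpha 0.05 two-sided and 200 subjects: section 9.7.2.2. Six on-treatment efficacy visits (11, 14, 15, 16, 17, 18): section 9.3.3; Table 7 places them at weeks 12, 26, 39, 52, 65 and 78, or months 2.77, 6, 9, 12, 15 and 18. Accrual is not stated. Assumption: uniform entry over A months, no dropout. The Synopsis gives Stage B about 42 months; less 18 of treatment and 3 of follow-up leaves at most 21, or about 18 after up to 3 months of prerandomization. I take 15–21 months as plausible and 12–36 as the outer range.

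**1. The protocol's own boundaries.** Lan-DeMets O'Brien-Fleming-type spending per side is α(t) = 2 − 2Φ(z/√t), with z = 2.241 for 0.025 per side. At t = 0.6, 2.241/√0.6 = 2.89, which spends 0.0038 per side, or 0.0076 two-sided. Solving recursively at 0.6/0.8/1.0 gives nominal p = 0.0076, 0.0221, 0.0423. The second and third match the protocol. The first does not: the printed 0.076 is ten times too large.

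**2. 18-month outcomes at the nominal looks.** At calendar month T, the share of subjects past the visit at month m is (T − m)/A, limited to 0–1. Set the sum over the six visits to 6 × 0.6 = 3.6 or 6 × 0.8 = 4.8. For A = 18:

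- 60%: the first visit is complete, so 1 + (5T − 60)/18 = 3.6 and T = 21.36. Share with an 18-month outcome: 3.36/18 = 18.7%, about 37 of 200, or some 12 per arm over three arms.
- 80%: the first two visits are complete, so 2 + (4T − 54)/18 = 4.8 and T = 26.1. Share: 8.1/18 = 45.0%.

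| Accrual (months) | At nominal 60% | At nominal 80% | Type I error, no borrowing |
|---|---|---|---|
| 12 | 2.5% | 35% | 6.5% |
| 15 | 12% | 40% | 6.3% |
| 18 | 18.7% | 45.0% | 6.1% |
| 21 | 24% | 49% | 6.0% |
| 24 | 29% | 51% | 5.9% |
| 36 | 39% | 59% | 5.6% |

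The last column applies 0.0076, 0.0221 and 0.0423 to a single contrast whose true information equals the completer share.

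The result depends on which visits are counted. At A = 18, including baseline gives 11.5% and 40%. Including the two follow-up visits (months 18.92 and 20.77) gives 1 + (7T − 99.69)/18 = 4.8, T = 24.0, 33%; and 3 + (5T − 84.69)/18 = 6.4, T = 29.2, 62%.

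**3. Boundaries matched to completers.** At true fractions 0.19 and 0.45, the same spending function gives about 5 × 10⁻⁷ and 0.0017, against the 0.0076 and 0.0221 that would be used.

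**4. Allowing for the MMRM.** Earlier visits carry partial information on month 18. With p_j the share of subjects whose last completed visit is j and Σ_j the covariance of their first j visits, total information is the sum of p_j Σ_j⁻¹, each padded with zeros to six visits. The fraction for the month-18 mean is then σ²₁₈ divided by the month-18 diagonal element of the inverse of that sum. The correlations are assumptions: compound symmetry 0.5–0.85, and autoregressive structures with variance growing over time.

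- A = 18: true information 0.28–0.55 and 0.58–0.82; matching first-look p 0.00004–0.005 and second-look p 0.006–0.024; type I error with the nominal boundaries 5.0–5.8%.
- A = 15 to 21: type I error 4.9–6.0%.

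**5. The misprint, for scale.** Using 0.076 at the first look gives a two-sided type I error of 9.7% even if the fractions truly are 0.6/0.8/1.0, and 11.7% at 0.19/0.45/1.0.

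**The case against.** The sentence says assessments without saying at which visits. Section 9.7.1.6 ties the early signal to ADCOMS at 18 months, so one could read it as 18-month assessments only, and the visit-mix problem would then vanish. A reader might infer that the protocol definitely counts every visit; the text does not go that far. What stands is that the literal words are unrestricted. Although section 9.7.1 leaves further detail to the SAP, the protocol has itself fixed this definition, and two analysts could time the looks and compute the boundaries differently from it.

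A reader might also infer that the boundaries are far too lenient and that the error necessarily exceeds 5%. The documents do not support that. The analysis is an MMRM, so completer share understates information, and with strongly correlated visits the inflation can vanish (5.0% at the high end of the correlations tried).

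Three further points stand. The looks are gated on MCI/Prodromal early success, so they may come later than the nominal fractions, or never; but early success can be declared from 200 randomized MCI/Prodromal subjects, so delay is not assured. The 5 mg arm is a minor contributor: Stage A targets 15 per arm across both cohorts, so at most about 15/200 = 7.5% of this cohort. And this is a secondary endpoint in a nested cohort of a Phase 2 study.

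**Conclusion.** The concern holds in limited form. The stated fraction is tied neither to the 18-month outcome nor to the compared arms, and it drives both the timing of the looks and the boundaries. On the literal reading with six on-treatment visits, fewer 18-month outcomes exist at the nominal 60% and 80% looks than those labels imply at every accrual period from 12 to 36 months: 2.5–39% and 35–59%, with 19% and 45% at 18 months.

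The effect on overall error is modest: about 6.1% at 18-month accrual with no borrowing, and about 5.0–5.8% with MMRM borrowing. The more practical harm is an 18-month efficacy claim resting on few 18-month outcomes. These figures assume uniform accrual, no dropout, a single contrast rather than the Dunnett pair, looks at exactly the nominal fractions, and illustrative correlations.

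The misprinted first boundary in the same section is numerically the larger error.

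**What to change.** In section 9.7.3, define the information fraction as the statistical information (inverse variance) for the month-18 MMRM contrast in placebo, 15 mg and 50 mg, divided by the information planned for that contrast at the final analysis. A simpler option is the number of mild to moderate AD subjects in those three arms with an observed, uncensored 18-month ADCOMS, divided by the number planned. The two are not equivalent: at 18-month accrual the completer count gives 0.19 at the first look where the MMRM information is 0.28–0.55, so the count is the more conservative. Choose one, and use it both to time the looks and to recompute the boundaries.

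Correct the first boundary from 0.076 to 0.0076 in sections 9.7.1.6 and 9.7.3 and in the Synopsis.

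The definition is a one-sentence change. Its cost is that both interim looks come later in calendar time; the inverse-variance version also needs a planned information value fixed in advance.
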